5. Potential Benefits and Importance of Information to be Gained. This study has several potential benefits. First, cancer patients with persistent pain randomized to the PCST-Community condition that learn ways to enhance their pain coping strategies may experience significant decreases in pain and disability. Cancer patients randomized to the mHealth-Ed condition may also gain important information about how to manage their pain and other aspects of their disease. Second, if the proposed PCST-Community protocol proves to be efficacious, it could be applicable to a number of patient populations with persistent pain who face challenges similar to breast cancer patients with persistent pain. Third, the proposed model of treatment delivery has the potential to be expanded to intervene on a number of other needs faced by patients with chronic illness (e.g., medication adherence, psychosocial distress, caregiver burden). This PCST-Community protocol model has the potential to dramatically increase access to treatment and improve patient outcomes.

Costs to the Subject

- Describe and justify any costs that the subject will incur as a result of participation; ordinarily, subjects should not be expected to pay for research without receiving direct benefit.

No cost to the subject.

Data Analysis & Statistical Considerations

- Describe endpoints and power calculations. Provide a detailed description of how study data will be analyzed, including statistical methods used, and how ineligible subjects will be handled and which subjects will be included for analysis. Include planned sample size justification. Provide estimated time to target accrual and accrual rate. Describe interim analysis including plans to stop accrual during monitoring. Phase I studies, include dose escalation schema and criteria for dose escalation with definition of MTD and DLT.

Statistical Power & Analyses. The approach to the analysis will utilize repeated measures mixed model analysis of covariance. For simplicity of exposition, this is described with the outcome not as a vector of 4 measurements, but instead as the analysis of a series of one-dimensional difference scores, with each difference score taken relative to the baseline measurement. Model covariates will include baseline score, variables unexpectedly unbalanced between groups at baseline (i.e., to account for potential bias), and variables that may be correlated with the outcome (i.e., to increase precision). Potential covariates include depression, social support, physical activity, medical/demographic variables including cancer treatments, and recruitment site.

Aim 1: Test the extent to which mPCST-Community reduces pain severity (primary outcome), pain interference, fatigue, physical disability, and psychological disability. Demographic, medical characteristics and other potential covariates will be summarized. Focusing on pain severity as an illustration of our analytical methods, we will first describe the pattern of missing data over time by group – paying particular attention to the possibility of differential drop-out. We will then analyze three outcome variables: post-intervention minus baseline addresses the mechanistic hypothesis pertaining to immediate effects of the intervention; 3 months minus baseline addresses the (primary) hypothesis of short-to-medium term effects of the intervention; and 6 months minus baseline addresses the hypothesis of longer-term effects of the intervention. Each hypothesis will be tested using the main effect of study group, adjusting for covariates. We anticipate relatively little missing data for the primary and mechanistic hypotheses – the issue of missing data will be addressed through sensitivity analyses using propensity scoring (which would essentially allow us to “compare likes with likes” even in the presence of differential drop-out).¹³⁰ **Statistical power.** For purposes of estimating power, we define pain severity as the primary outcome variable. Using the methods of Cohen, and assuming an effective sample size of 72 per group (i.e., 90 per group minus 20% attrition), an unadjusted analysis has 80% power to detect an effect size of approximately 0.48. This is a moderate effect size which is a reasonable estimate of the minimum clinically important difference in patients with pain and practically important and consistent with what will need to be shown for adoption of the intervention in clinical practice.¹³¹⁻¹³³ Further support for this effect size is gained from our pilot work that has been consistent (within the constraints

imposed by study design and sample size) with an intervention having this level of efficacy.¹ In an unadjusted analysis, the effect size equals the difference between the group means divided by the pooled standard deviation. (Consistent with previous data, this could for example be a difference in mean pain scores of 5.0 vs 4.0; SD= 2.0). Such a power calculation is conservative, as the reduction in degrees of freedom associated with the covariates in an adjusted analysis should have less of an impact than the reduction in the mean squared error associated with those same covariates.

Aim 2: Explore potential mediators (i.e., self-efficacy for pain control, pain catastrophizing) through which mPCST-Community leads to reduction in pain severity, pain interference, fatigue, physical disability, and psychological disability. This hypothesis will be explored, for example, by first fitting a model with intervention group as the primary predictor and self-efficacy as an outcome, and then by fitting a second model with self-efficacy as the primary predictor and pain severity as an outcome. Including intervention group in this latter model also allows us to test an interaction between self-efficacy and intervention group and, thus, assess whether the relationship between self-efficacy and pain severity is consistent across study groups. In contradistinction with the other analyses associated with this aim, the test for interaction is likely to have modest power and thus is considered to be exploratory. The same caveat applies to other interactions – for example, for aim 1 a test of whether the impact of the intervention is consistent across gender or other similarly-defined patient subgroup. This approach to mediator analyses is appropriate given the relative lack of maturity of the science examining interactions within behavioral intervention trials; while this study is designed around main effects, Aim 2 provides adequate new knowledge within the practical constraints of this trial. This approach to mediation analyses is consistent with current analysis of RCTs from the biomedical literature.¹³⁴⁻¹³⁶

Aim 3: To evaluate cost, cost-effectiveness and practicality of mPCST-Community. **Analyses.** We will use patient-level data to test for differences between mPCST-Community and the Health-Edu conditions on medical resource use, medical costs and productivity costs. We will use generalized linear models specified using negative binomial error distributions and log links for resource use and gamma error distributions and log links for costs. We will apply mixed-effects linear regression models to test for interactions between study interventions and time on EQ-5D-derived preference weights across the 6-month follow-up period. Baseline resource use and EQ-5D weights will be included as covariates in regression models. For each patient will compute quality-adjusted life-years (QALY) using the trapezoidal rule applied to EQ-5D weights at baseline, post-intervention, 3 months and 6 months. Because the mHealth-Ed control was designed to control for patient contact time and does not represent standard care, accounting for the costs of providing this condition and patient time spent participating would inappropriately offset the costs associated with the mPCST-Community intervention. Therefore, we will modify our calculation of the numerator of incremental cost-effectiveness ratio (ICER) in which we will calculate the difference in mean medical costs and productivity costs between the mPCST-Community and mHealth-Ed control groups then add direct costs of resources required to provide mPCST-Community as well as participant time costs. To compute the difference in QALYs, we will subtract mean QALYs in the mHealth-Ed condition from mean QALYs in the mPCST-Community condition. Then, we will divide the estimated difference in mean costs by the difference in mean QALYs and generate a 95% confidence interval constructed using nonparametric bootstrapping. We then will calculate net health benefits (QALY* λ – Cost, where λ represents maximum willingness to pay per QALY) for each patient, and apply linear regression analysis to evaluate whether intervention and patient baseline characteristics are associated with improved cost-effectiveness. In sensitivity analyses, we will evaluate the impact of: (1) applying various durations of sustained benefit beyond the 6-month follow-up period; (2) excluding productivity gains/costs; and (3) assuming patients could participate in videoconferencing at home. To evaluate practicality and sustainability of PCST-Community, we will assess accrual, participant retention, and intervention protocol adherence.

Data & Safety Monitoring

- Summarize safety concerns, and describe the methods to monitor research subjects and their data to ensure their safety, including who will monitor the data, and the frequency of such monitoring. If a data monitoring committee will be used, describe its operation, including stopping rules and frequency of review, and if it is independent of the sponsor (per 45 CFR 46.111(a) (6)).

This behavioral pain intervention trial carries minimal risk. All patients in the trial will continue their usual care during the course of trial, thus their doctors will provide monitoring of the patients' overall medical status. All research personnel who have direct contact with patients will be trained to observe and report any adverse event to the principal investigator. The principal investigator will report any adverse events to the institutional review board at Duke University within 48 hours. An adverse event is defined as any untoward medical occurrence during the clinical investigation that has a causal relationship to the study protocol. A serious adverse event is defined as any event which results in death, is immediately life threatening, results in persistent or significant disability/incapacity, patient hospitalization, or is serious for

any other reason representing significant hazard. We will also appoint two data safety officers. One data safety officer will be a MD who is not associated with this study. The appointed MD officer will have experience with clinical research and trials and have a thorough understanding of adverse events. The other safety data officer will be a senior investigator who has technology expertise and will have an annual responsibility to evaluate our current mHealth system of assessment and intervention and identify any problems. All adverse events will be reported to Duke's IRB and the data safety officer in real time. All data will be stored on a secure server with multiple backups created regularly. All interactions with study participants will be under the direction of a Licensed Clinical Psychologist ([name] [PI]). Study investigators and staff for this trial will be taught to monitor for any signs that participants are experiencing high levels of physical or emotional distress that need to be addressed outside the context of this trial. If this is determined to be the case, the PI will work directly with the participant to move forward in a way that is in the best interest of the patient. No participant will be kept in the trial if they are experiencing increased extreme distress. [name] works directly with Cancer Patient Support and Care at Duke Cancer Institute as a practicing licensed clinical psychologist and as a supervisor to psychology trainees (i.e., advanced graduate students, clinical psychology interns); she is integrated into the psychosocial care program at the Cancer Center and has experience referring cancer patients who are distressed to appropriate psychosocial or psychiatric care within this large team of mental health professionals. She will use the same resources when making referrals for distress participants in this study.

Privacy, Data Storage & Confidentiality

- Complete the Privacy and Confidentiality section of the iRIS submission form.

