Guided by extensive prior work, we have designed an innovative mHealth behavioral pain coping skills training (PCST) intervention to reduce pain and disability in cancer patients in medically underserved areas (mPCST-Community). Our prior work has tested PCST protocols through in-person sessions at major medical centers where resources and literacy levels are relatively high. mPCST-Community is different and innovative; it uses mHealth technology (e.g., videoconferencing) to decrease access barriers for patients in medically underserved areas. The protocol is brief (4 sessions) and delivered in the community clinic by a remote well-trained pain therapist. Importantly, this protocol has been carefully adapted for low literacy patients. [name], a nationally recognized expert in strategies for adapting pain coping interventions to low literacy, medically underserved patients, was instrumental in developing the mPCST-Community protocol. mPCST-Community extends to the patient's daily life through use of a simple mobile application that provides low literacy text/audio protocol summaries, relaxation audio, daily assessment and personalized feedback, and coping messaging.

We propose a randomized controlled trial (RCT) to test the efficacy of the developed mPCST-Community protocol in breast cancer patients with pain receiving cancer care in medically underserved areas (N=190). We have done careful and extensive pilot work to prepare for the proposed trial. Our pilot work (*Journal of Psychosocial Oncology*) was conducted in breast cancer patients with pain in three medically underserved rural community clinics. First, focus group data (3 groups; n=19) were used to further refine the adapted protocol. Second, the mPCST-Community protocol was evaluated in a single-arm trial with 20 patients. We found high feasibility (i.e., recruitment met), low attrition and high adherence (90% completion), and high acceptability. Importantly, impressive and positive pre- to post-intervention changes were found for pain severity ($t=-2.52$, $p=0.01$, $g_{av}=0.62$; 30% change), pain interference ($t=-2.62$, $p=0.01$, $g_{av}=0.62$), and self-efficacy for pain management ($t=3.57$, $p=0.0004$, $g_{av}=0.98$; 30% change).⁸ Study specific aims are:

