Behavioral cancer pain interventions are minimal to absent in medically underserved areas.⁵⁴ To date, these interventions are typically conducted through in-person sessions with well-trained pain therapist at a major medical center. Primary barriers to accessing in-person behavioral interventions include time constraints, transportation difficulties (e.g., availability, parking), and distance from the medical center.⁵⁵ Cost factors (e.g., financial, time, physical) also pose intervention access barriers.^{56,57} Additional barriers contribute to the absence of behavioral cancer pain intervention for patients in

underserved areas including lack of trained pain therapists at community-based clinics, prohibitive travel to major medical centers, and low literacy levels. Breast cancer patients who reported higher levels of time, effort, and cost barriers to needed treatment reported lower levels of functional and psychological well-being⁵⁸ both of which can increase pain and disability.

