mHealth Behavioral Cancer Pain Intervention (mPCST-Community). Participants will complete 4, 50-minute video-sessions at their community-based clinic; a therapist at Duke will deliver the session. Participants may also choose to complete their 4, 50-minute video-sessions in their home environment. Staff will be present at the community-based clinic to assist. Each site has a private room where the videoconferencing sessions will be conducted; we have used 3 of the proposed sites in our pilot studies and have successfully

set up the videoconferencing systems. mPCST-Community includes a mobile app to extend the intervention into daily life.

The therapist delivering the mHealth behavioral cancer pain intervention will be a doctoral level clinical psychologist. Once the video connection has been established, the patient and therapist will complete a session that mimics an in-person, face-to-face session. mPCST-Community sessions will be scheduled weekly with some flexibility (8 weeks to complete sessions) provided for scheduling conflicts (e.g., sickness, holidays). The content of the mHealth behavioral cancer pain intervention sessions is based on Pain Coping Skills Training (PCST) designed by [name] (Co-I). [name], along with Drs. [name], [name], and [name], has carefully designed the proposed mHealth protocol choosing particular skills shown to be efficacious in patients with cancer pain; further the protocol has been carefully designed to include content relevant to patients in medically underserved areas. PCST enhances patients ability to cope with their pain by teaching them skills to enhance their ability to manage their pain by changing their behaviors, thoughts, and feelings about pain.⁸⁹ Also, based data gathered from focus groups, the intervention protocol has been updated throughout to address fatigue as it relates to pain. We expect that the skills in this protocol will enhance patients' ability (i.e., self-efficacy): a) to use attention diversion techniques to decrease pain and distress, b) manage their pain to engage in activities that will decrease their pain, disability, and distress, and c) to use cognitive restructuring to decrease pain catastrophizing which can result in decreased pain, disability, and distress.

Selection of Subjects

- List inclusion/exclusion criteria and how subjects will be identified.

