Participants. Participants will be women with a diagnosis of breast cancer within the last three years. Stages I-IV will be included as recently published work suggests increased life expectancy for patients with advanced cancer⁸⁷ and significant pain is possible from both the tumor and cancer treatments during this time period.¹⁹⁻²³ Other eligibility criteria are: 1) being ≥ 18 years old, 2) having a life expectancy of ≥ 12 months, 3) report experiencing pain on at least 10 days in the last month and rate their pain in the past week as a 4 or greater on a 0-10 scale. The combination of these items assess patients level of persistent pain (in the last month) and pain severity with an accurate recall period (i.e., last week; ≥ 4). Exclusion criteria include: 1) cognitive impairment as indicated by a baseline Folstein Mini-Mental Status Examination of <25 ⁸⁸ and the Rapid Estimate of Adult Literacy in Medicine, Revised (REALM-R) or through medical chart review indicated by a baseline Folstein Mini-Mental Status of Examination <25 2) brain metastases, 3) presence of a severe psychiatric condition or a psychiatric condition (e.g., suicidal intent) that would contraindicate safe participation in the study as indicated by the medical chart, treating oncologist, or medical/study staff interactions, or 4) current or past (<6 months) engagement in PCST for cancer.

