Recruitment. Participants will be recruited from cancer clinics that are part of the Duke Cancer Network (DCN). Each clinic is in a medically underserved area and sites are in mostly rural or highly urban areas of North Carolina, South Carolina, Georgia, and Virginia and has provided a detailed letter of support. These clinics provide oncology care to patients who otherwise would have very limited access to subspecialty cancer care. We will recruit from 8 sites (see Table 2 for site, county consensus, the medically underserved index, primary care physician to patient ratio, annual number of breast cancer patients, and projected annual and total recruitment). Each clinic has staff designated to assist with trial recruitment (see letters of support from site oncologists). During study start-up, the study team will travel to each site to train staff members in procedures. Training may also take place over a videoconferencing platform. Short videos along with written information on study purpose and procedures will be produced and available to clinic staff at each site. Study staff will visit each site at least quarterly and up to twice quarterly. Our team consists of several experienced clinical trials investigators with extensive histories of successful recruitment (Drs. [name], [name], [name]). Drs. [name] (PI) and [name] (Co-I) have successfully recruited breast cancer patients to behavioral trials in the DCN clinics. The study team will closely track participant recruitment during the first year of recruitment. If recruitment is not met at 90% overall for Year 1, three of our sites (i.e., Gwinnett, Lexington, Spartanburg) have indicated that they will work with our team to increase recruitment (see letters of support; 40 additional patients annually).

We will use electronic medical records (EMR), tumor registry information, and clinic staff to identify potential patients. The clinical research coordinator will send an email to the treating oncologist to alert them of potential participants. Participating oncologists have agreed to alert the study team if they estimate a potential participant has less than 1-year to live or there is known psychotic disorder, suicidal

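### Exclusion 4 allows women already trained in the test intervention to be randomised once six months have passed; the likely loss of power is small and the remedy is cheap

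*Combined protocol and SAP*

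**What the plan says.** Under Selection of Subjects (Participants), the fourth exclusion is "current or past (<6 months) engagement in PCST for cancer". It is the only eligibility rule about earlier training, and no reason is given for the six months.

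Other sections bear on it:

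- **Purpose of the Study:** "the mPCST-Community protocol was evaluated in a single-arm trial with 20 patients", among breast cancer patients with pain in three rural clinics.
- **Design & Procedures (mPCST-Community):** "we have used 3 of the proposed sites in our pilot studies".
- **Selection of Subjects (Recruitment):** members of the team "have successfully recruited breast cancer patients to behavioral trials in the DCN clinics". The number of those trials, and whether they used PCST, is not stated. Candidates for the present trial are found through medical records, tumor registries and clinic staff.
- **Data Analysis, Aim 1, primary contrast:** "3 months minus baseline addresses the (primary) hypothesis of short-to-medium term effects of the intervention". The last assessment carries a separate hypothesis, worded in the same section as follows: "6 months minus baseline addresses the hypothesis of longer-term effects of the intervention".
- **Data Analysis, Aim 3:** one cost-effectiveness sensitivity analysis is "applying various durations of sustained benefit beyond the 6-month follow-up period".
- **Data Analysis, opening paragraph:** the potential covariates named do not include prior PCST.

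**The concern.** By excluding recent PCST, the plan accepts that earlier training can blur the comparison. The question is whether six months is enough. Aim 1 tests whether benefit is still present 6 months after the intervention. A woman trained a little over six months ago would enter at about the point where the trial hypothesises that an effect persists.

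The women concerned can be identified. The pilot gave 20 patients the same intervention, trial sites overlap with pilot sites, and registry searches could list those patients again. The pilot is already reported, so its participants may well be past the six-month limit. That is an inference, because no pilot dates are given.

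A previously trained woman assigned to mHealth-Ed is a control with some of the active training. Assigned to mPCST-Community, she repeats four sessions she has already had. If the repeat brings less than the first course did, she contributes less than a new participant to the difference the trial is sized to detect.

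**Working it through.** **Window against horizon.** The look-back is 6 months. The primary time point is 3 months after the intervention and the longest tested one is 6 months. The window therefore exceeds the first and equals the second.

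**Inputs for the size of the effect**

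| Input | Value | Source |
|---|---|---|
| Randomised | 190, equal allocation | Research Plan |
| Evaluable per group | 72 (90 less 20%) | Aim 1, statistical power |
| Effect size | 0.48 at 80% power | Aim 1, statistical power |
| Pilot patients trained | 20 | Purpose of the Study |
| Significance level | two-sided 0.05 | assumed; not stated |
| Previously trained women, k | 0 to 20 from the pilot | assumed range; no prevalence given |
| Share of the normal gain they obtain, r | 0, then 0.5 | assumed |

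**The plan's own figure.** For a two-sample t-test with n = 72 per group there are 142 degrees of freedom and the critical value is 1.977. The noncentrality is d × √(n/2) = 0.48 × √36 = 2.88. Power is 81.6%, and the effect detectable with 80% power is 0.470. The stated 80% at about 0.48 is reproduced to within 2 points.

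**Dilution.** Suppose k of the 190 women were trained before, are spread evenly over the arms, drop out at the same rate as the others, and leave the SD unchanged. Then

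d(k) = 0.48 × [1 − (k/190) × (1 − r)].

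With r = 0 (no further gain) and 72 per group:

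| k | k/190 | d(k) | Power |
|---|---|---|---|
| 0 | 0% | 0.480 | 81.6% |
| 2 | 1.1% | 0.475 | 80.8% |
| 5 | 2.6% | 0.467 | 79.5% |
| 10 | 5.3% | 0.455 | 77.3% |
| 20 | 10.5% | 0.430 (0.48 × 170/190) | 72.6% |

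Power reaches 80% when d = 0.470, that is when k/190 = 1 − 0.470/0.48 = 2.1%, or about 4 women.

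**Sensitivity to the assumptions**

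- *Half the normal gain (r = 0.5), 72 per group:* 80.6% with 5 women and 77.3% with 20.
- *Group size implied by N = 190:* 95 per group, or 95 × 0.8 = 76 after attrition. With r = 0, power is 83.6% with none, 81.7% with 5 and 74.9% with 20.
- *Starting from the plan's illustration of 5.0 against 4.0 with SD 2.0 (d = 0.50), 72 per group, r = 0:* 80.6% with 10 and 76.0% with 20.

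**The case against.** The strongest reply is that the problem is nearly empty. To re-enter, a pilot participant must still be within three years of diagnosis, have had pain on at least 10 days in the last month, rate it 4 or more, and agree to take part again. The older the pilot, the fewer women remain inside the diagnosis window. Outside the pilot, the Background states: "Behavioral cancer pain interventions are minimal to absent in medically underserved areas". With one or two such women, power stays above 80%. The group size implied by N = 190 adds a small cushion. All of this stands, and it is why the point is minor in size.

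Second, outcomes are changes from baseline with the baseline score as a covariate, so a stable carry-over is already in a woman's baseline in either arm. This also stands. Attenuation needs a smaller *further* gain on retraining. That is plausible, but the documents do not establish it.

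A reader might infer three stronger points:

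- **That the window is shorter than the benefit the trial expects.** The documents do not support this. The window equals the longest tested horizon, and benefit beyond 6 months appears only as a cost-effectiveness scenario.
- **That the trial is biased toward no effect.** Randomisation should balance prior exposure on average. The dilution depends on an unknown number of women and an unknown retraining gain. A former participant might recognise her arm, but that could move self-reported pain either way, and the text makes no claim that participants are blinded.
- **That PCST for any other pain condition must also be excluded.** That would rest on long recall and narrow the sample without a shown gain. It is a debatable trade-off, not a defect.

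The reply does not answer the gap itself. The criterion admits past recipients of the test intervention, and the plan gives no reason for doing so.

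**Conclusion.** The concern holds in a limited form. Exclusion 4 permits randomisation of women who received PCST for cancer, including mPCST-Community itself, six or more months earlier. The six-month window is no longer than the benefit tested in Aim 1, and prior PCST is not among the listed covariates.

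The consequence is possible attenuation of the between-group difference, not imbalance between arms. On the least favourable assumption of no further gain, a handful of such women costs about 2 points of power (81.6% to 79.5% with 5). The fall to 72.6% requires all 20 pilot patients to re-enrol and none to gain again, which the eligibility criteria make unlikely. These figures assume two-sided 5%, 72 evaluable per group and even spread over the arms. The actual number of previously trained women cannot be derived from the documents.

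The case for changing the rule rests on its low cost, not on a demonstrated material loss.

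**What to change.** Reword exclusion 4 as: *any current or prior engagement in PCST for cancer, including participation in the mPCST-Community pilot trial*. At the sites used in the pilot studies, check each screening list against the pilot participant list before randomisation.

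The cost is a short amendment, one screening question and a comparison with a list of 20 patients. The downside is the loss of a few otherwise eligible women. By the plan's own account of how scarce such training is in these areas, the number should be very small.

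If the sponsor prefers to keep the six-month window, the protocol should give the reason for it, state whether pilot participants are eligible, and record any prior PCST at baseline so that a sensitivity analysis can leave those women out.
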